Post Authorization Safety Study (PASS) Information

Acronym/Title	HA-SAFE: Observational study evaluating long-term safety of real-world treatment with damoctocog alfa pegol in previously treated patients with hemophilia A
Protocol version and date	v 1.0, 13 JAN 2020
IMPACT study number	20904
Study type / Study phase	Observational, post-approval  PASS Joint PASS:  YES  NO
EU PAS register number	Study not yet registered
Active substance	ATC code: B02BD02/Hematological/Damoctocog alfa pegol
Medicinal product	Jivi
Product reference	EU/1/18/1324/001 Jivi 250 IU; EU/1/18/1324/002 Jivi 500 IU; EU/1/18/1324/003 Jivi 1000 IU; EU/1/18/1324/004 Jivi 2000 IU; EU/1/18/1324/005 Jivi 3000 IU
Procedure number	EMA/H/C/004054
Study Initiator and Funder	Bayer Consumer Care AG, Basel, Switzerland
Research question and objectives	
The aim of this study is to characterize in a real-world setting the long-term safety of damoctocog alfa pegol drug usage.
 
The primary objective of this study is to assess the long-term safety of prophylaxis with damoctocog alfa pegol in patients with hemophilia A in the real-world setting through the collection and analysis of adverse events (AEs) of special interest including those potentially indicative of PEG accumulation (hypersensitivity reactions, loss of drug effect, renal impairment, neurocognitive disorders, and inhibitor development), AEs, serious adverse events (SAEs), and adverse reactions (ARs).
 
The secondary objective is to monitor the clinical effects of long-term exposure of prophylaxis damoctocog alfa pegol in

	patients with hemophilia A, including assessments of kidney and liver function parameters, neurological function and patients' PEG plasma levels.
Country(-ies) of study	The study will be conducted in Europe, countries are not yet identified. Potential countries are Austria Belgium/Luxemburg, Finland, Germany, Greece, Italy, Netherlands, Portugal, Scandinavia (Denmark, Norway, and Sweden), Slovenia, Spain, and Switzerland. The study may also be conducted in other countries not currently listed.
Author	PPD [REDACTED] PPD [REDACTED]

Marketing authorization holder

Marketing authorization holder(s)	Bayer AG 51368 Leverkusen, Germany
MAH contact person	PPD [REDACTED] PPD [REDACTED] PPD [REDACTED]

The study will be conducted in compliance with the protocol and any applicable regulatory requirements.

Table 2:	Overview of information collected during the initial visit and at subsequent follow-up visits.....	20
Table 3:	List of stand-alone documents	39

2. List of abbreviations

AE	Adverse Event
ALT	Alanine Aminotransferase
AR	Adverse Reaction
AST	Aspartate Aminotransferase
BDD-rFVIII	B-domain-deleted recombinant factor VIII
CFR	Code of Federal Regulations
CRA	Clinical Research Associate
CRO	Contract Research Organization
CRP	C-Reactive Protein
DMP	Data Management Plan
EDC	Electronic Data Capture
EFPIA	European Federation of Pharmaceutical Industries and Associations
eCRF	Electronic Case Report Form
eGFR	Estimated Glomerular Filtration Rate
EMA	European Medicine Agency
ENCePP	European Network of Centers in Pharmacoepidemiology and Pharmacovigilance
EU	European Union
FDA	US Food and Drug Administration
FVIII	Factor VIII
GGT	Gamma-Glutamyl Transferase
GPP	Good Publication Practice
GVP	Good Pharmacovigilance Practice
ICH	International Council for Harmonisation
IEC	Independent Ethics Committee
IRB	Institutional Review Board
IU	International Units
MAH	Marketing Authorization Holder
MedDRA	Medical Dictionary for Regulatory Activities
MRP	Medical Review Plan
PAS	Post-Authorization Study
PASS	Post-Authorization Safety Study
PRAC	Pharmacovigilance Risk Assessment Committee
pCRF	Paper Case Report Form
PEG	Polyethylene Glycol
PK	Pharmacokinetic
PT	Preferred Term
PTPs	Previously Treated Patients
QPPV	Qualified Person Responsible For Pharmacovigilance
QRP	Quality Review Plan
rFVIII	Recombinant factor VIII

SAE	Serious Adverse Event
SAF	Safety Analysis Set
SAP	Statistical Analysis Plan
SOC	System Organ Class
STROBE	Strengthening the Reporting of Observational Studies in Epidemiology

3. Responsible parties

3.2 Collaborators/Committees

Contact details on the coordinating and/or principal investigators, co-investigators and other site personnel for each country and site participating in the study are listed in a stand-alone document (see [Table 3](#)) which is available upon request.

Administrative changes of responsible persons and/or the composition of the committees will be documented by updating the respective lists, but do not require formal protocol amendments.

4. Abstract

Acronym/Title	HA-SAFE: Observational study evaluating long-term safety of real-world treatment with damoctocog alfa pegol in previously treated patients with hemophilia A
Protocol version and date	v 0.5, 26 AUG 2019
IMPACT study number	20904
Study type / Study phase	Observational, post-approval  PASS Joint PASS:  YES  NO
Author	PPD [REDACTED]
Rationale and background	
Hemophilia A is an X-linked, inherited, genetic bleeding disorder characterized by the deficiency of clotting factor VIII (FVIII). Hemophilia A comprises approximately 80% of all hemophilia cases, with an annual incidence of approximately 1 in 5,000 live male births. All races and economic groups are affected equally. Prevalence estimates vary by country, ranging between 5 and 21 cases per 100,000 male births.
 
Damoctocog alfa pegol is approved for prophylaxis and treatment of bleeds in previously treated patients (PTPs) with hemophilia A aged ≥ 12 years, with a two times per week, every 5 days or every 7 days dose that allows for the treatment regimen to be tailored to individual patient needs. Efficacy and safety of prophylaxis dosing with damoctocog alfa pegol were demonstrated in 2 phase II/III clinical studies in adult, adolescent, and pediatric (< 12 years of age) PTPs with severe hemophilia A.
 
The aim of this observational study is to characterize in a real-world setting the long-term safety of damoctocog alfa pegol drug usage. These results will elucidate the safety profile of real-world prophylaxis with damoctocog alfa pegol.
 
Patients and physicians participating in HA-SAFE can choose from 3 effective prophylaxis regimens with damoctocog alfa pegol based on individual patient bleeding profile and lifestyle. However, outside of the clinical study, there are currently little real-world safety data on the use of the product.


Research question and objectives
	
The aim of this study is to characterize in a real-world setting the long-term safety of damoctocog alfa pegol drug usage.
 
Primary objective is:
 
 To assess the long-term safety of prophylaxis with damoctocog alfa pegol in patients with hemophilia A in the real-world setting through the collection and analysis of adverse events (AEs) of special interest including those potentially indicative of PEG accumulation (hypersensitivity reactions, loss of drug effect, renal impairment, neurocognitive disorders, and inhibitor development), AEs, serious adverse events (SAEs), and adverse reactions (ARs). 
Secondary objective is:
 
 To monitor the clinical effects of long-term exposure of prophylaxis damoctocog alfa pegol in patients with hemophilia A, including assessments of kidney and liver function parameters, neurological function and patients' PEG plasma levels.

Study design
	
HA-SAFE is a multinational, open-label, prospective, non-interventional, multicenter, cohort study of PTPs with hemophilia A receiving damoctocog alfa pegol as prophylaxis treatment. The study is planned to be conducted in multiple countries in Europe.
 
At study start, retrospective data will be collected on the patients' medical condition and hemophilia treatment history. Also at study start and then at each physician visit during the follow-up phase, data will be recorded on regimens used, AEs of special interest including hypersensitivity reactions, loss of drug effect, renal impairment, neurocognitive disorders, and inhibitor development, other AEs, SAEs and drug-related ARs in standard clinical practice. Adverse reactions (ARs) relating to the system organ classes of the nervous system and psychiatric disorders will be recorded.
 
The planned observation period for each of at least 50 patients will be 4 years, all patients will stay in the study until completion of the overall study.
 
Data collection will occur continuously throughout the patient's observational period (i.e., each visit or assessment will be documented in the eCRF/EDC system as they occur).

Population
	
All PTPs with hemophilia A receiving prophylaxis with damoctocog alfa pegol will be eligible to be enrolled in the

	
study. Indications and contra-indications according to the local market authorization will be carefully considered
 
Inclusion criteria:
 
 • Signed informed consent/assent will be obtained before any study-related activities (i.e. any procedure related to the recording of data according to the protocol) • PTPs with hemophilia A assigned to Jivi prophylaxis treatment • Negative FVIII inhibitor test before study entry • Decision to initiate treatment with commercially available Jivi has been made by the treating physician before and independently from the decision to include the patient in this study 
Exclusion criteria:
 
 • Known or suspected contraindications to Jivi or related products • Mental incapacity, unwillingness or other barriers precluding adequate understanding or cooperation • Participation in an investigational program with interventions outside of routine clinical practice

Variables
	
The variables for the primary objective are:
 
 • Diagnosis of AE or symptom (if diagnosis unknown). • Qualification as AE of special interest including hypersensitivity reactions, loss of drug effect, renal impairment, neurocognitive disorders, and inhibitor development. • Start and stop date. • Seriousness. • Reasonable causal relationship to damoctocog alfa pegol treatment. • Action taken. • Event outcome. • Other specific treatment(s) of AE. • Date of inhibitor measurement (if collected). • Inhibitor (no/yes) (if collected). • Titer of inhibitor (Bethesda units) (if collected).

	
The variables for the secondary objective are:
 
Laboratory parameters (including date of test), if collected in routine clinical practice at the physician’s discretion:
 
 • Biochemistry parameters: 
 ○ Sodium, potassium, albumin, creatinine, bilirubin, aspartate aminotransferase (AST), alanine aminotransferase (ALT), gamma-glutamyl transferase (GGT), alkaline phosphatase, C-reactive protein (CRP), urea, estimated glomerular filtration rate (eGFR). • Urinalysis parameters: 
 ○ Urine albumin/creatinine ratio and spot urine dipstick test. • PEG plasma levels 
Parameters for neurological assessments to be documented if available include the following:
 
 • Date of assessment • Level of consciousness, cranial nerves, body tone, strength (of the four extremities), reflexes, sensory aspects, gait, coordination and fine motor function, mental state. • For children: evaluation of appearance, language, social interaction.

Data sources
	
Historical data based on medical records or on information provided by the patient during routine clinical visits. Treatment-related data documented during visits that take place in routine practice.

Study size
	
The study aims to observe 50 patients for at least 4 years each. Assuming a dropout rate of approximately 20% (due to lost to follow-up cases or withdrawals), 60 patients will be enrolled.

Data analysis
	
Statistical analyses will be of an explorative and descriptive nature. The study is not aimed to confirm or reject predefined hypotheses; hence no formal hypothesis testing will be performed.
 
All variables will be analyzed descriptively with appropriate statistical methods: categorical variables by frequency tables (absolute and relative frequencies) and continuous variables by sample statistics (i.e., mean, standard deviation [SD], minimum, median, quartiles, and maximum). Continuous

	variables will be described by absolute value and as change from baseline per analysis time point, if applicable.
Milestones	First patient first visit: Q2 2020 Last patient first visit: planned Q2 2023 Last patient last visit: planned Q2 2028 Final report: planned Q4 2028

5. Amendments

None.

6. Milestones

Table 1 presents the planned milestones for the project. These milestones are based on a timely review and approval of the project. Administrative changes to milestones due to delays in study preparation and enrolment do not require amendments to the protocol. Revised study timelines and milestones which do not constitute a need for a formal protocol amendment are kept as stand-alone document (Table 3) that is available upon request.

Table 1: Milestones

Milestone	Planned date
Start of data collection (First Patient First Visit)	Q2 2020
End of data collection (Last Patient Last Visit)	Q2 2028
Annual Interim Report	2021 - 2027
Registration in the EU PAS register	Q2 2020
Database clean	Q3 2028
Final statistical analysis	Q4 2028
Final report of study results	Q4 2028

7. Rationale and background

7.1 Epidemiology, classification, and treatment of hemophilia A

Hemophilia A is an X-linked, inherited, genetic bleeding disorder characterized by the deficiency of clotting factor VIII (FVIII) [1],[2]. Hemophilia A comprises approximately 80% of all hemophilia cases, with an annual incidence of approximately 1 in 5,000 live male births [1],[2]. All races and economic groups are affected equally [2]. Prevalence estimates vary by country, ranging between 5 and 21 cases per 100,000 male births. According to the World Federation of Hemophilia, it is estimated that only between 25% and 30% of hemophilia patients globally are adequately diagnosed and managed [3]. Furthermore, up to 75% of hemophilia patients globally live in developing countries in which access to specialist health care professionals and modern therapies prove to be a substantial barrier.

Normal FVIII levels vary between 50% and 150%. The severity of hemophilia A is classified by the amount of clotting factor present in the blood: mild, if the patient has >5% normal clotting factor (>0.05 international units [IU]/mL); moderate, if the patient has between 1% and 5% (≥ 0.01 to 0.05 IU/mL) normal clotting factor; and severe, if the patient has <1% (<0.01 IU/mL) normal clotting factor. Patients with mild or moderate hemophilia A typically have bleeds only following trauma and tend to report fewer major health-related quality of life impacts. It is estimated that between 60% and 70% of patients with hemophilia A have the severe form of the disease [4]. For these patients, bleeding events often spontaneously occur in joints or muscles or with minimal or unknown trauma to the affected area [5]. Recurrent bleeding in the joints can lead to progressive joint damage, loss of joint mobility, and chronic pain.

The two main approaches to treatment are on-demand therapy, in which the patient is treated in response to a bleed, or prophylactically, in which the patient is treated regularly to prevent bleeding episodes. Prophylaxis is now considered the standard of care in many countries, especially in the pediatric and adolescent population, as it has been shown to reduce complications from repeated bleeds, particularly joint arthropathy [1].

7.2 Rationale

Damoctocog alfa pegol is a B-domain–deleted recombinant factor VIII (BDD-rFVIII) that is site-specifically conjugated with a 60-kDa branched polyethylene glycol (PEG) molecule at a cysteine that has been introduced into the A3 domain (K1804C) resulting in 1 PEG per BDD-rFVIII protein [6]. This addition of PEG prolongs the duration of FVIII in circulation while retaining its full coagulant activity [7],[8]. Damoctocog alfa pegol (Jivi) is approved for prophylaxis and treatment of bleeds in previously treated patients (PTPs) with hemophilia A aged ≥ 12 years, with a two times per week, every five days or every seven days dose that allows for the treatment regimen to be tailored to individual patient needs. An enhanced pharmacokinetic (PK) profile enables a potentially decreased dosing frequency compared with unmodified rFVIII. Efficacy and safety of prophylaxis dosing with damoctocog alfa pegol were demonstrated in 2 phase II/III clinical studies in adult, adolescent, and pediatric (<12 years of age) PTPs with severe hemophilia A [9],[10].

The aim of the proposed study is to characterize in a real-world setting the long-term safety of damoctocog alfa pegol drug usage. The study design will allow for fulfilling the post-approval commitment to the European Medicines Agency (EMA). In accordance with the EMA requirements regarding sample size and observation time, the study aims to observe 50 patients for at least 4 years

each. Detailed information will be collected on reported adverse events (AEs) of special interest including hypersensitivity reactions, loss of drug effect, renal impairment, neurocognitive disorders, inhibitor development, and serious adverse events (SAEs). These parameters will assess if there are any potential safety risks of long-term PEG exposure. The AEs of hypersensitivity and loss of drug effect are related to the class of FVIII replacement therapy. Since damoctocog alfa pegol is a PEGylated product, immunogenicity related to the PEG component can occur. Although the 60 kDa PEG that is part of the damoctocog alfa pegol molecule is larger than the 20-40 kDa PEG moieties on other FVIII replacement products, the low content of PEG associated with the site-specific PEGylation of damoctocog alfa pegol results in a lower PEG load (PEG amount per treatment or per week) and consequently in plasma and tissues relative to some other PEGylated products. The preclinical toxicology studies demonstrated an absence of any pathological effects. The low peak plasma level of approximately 0.1 mg/L at steady state in humans is consistent with these pre-clinical data. No increase in PEG plasma levels has been observed in the clinical studies including the extension studies in more than 100 patients with a total treatment period of at least 3 years up to 6 years¹.

The results of this observational study aim to add to the knowledge of the safety profile of real-world prophylaxis with damoctocog alfa pegol.

Prior to finalization of the present HA-SAFE protocol v1.0, protocol version 0.5 was endorsed by the PRAC on 28 November 2019 (as confirmed in the outcome letter dated 05 December 2019).

7.3 Background

Prophylaxis with FVIII reduces bleeds and improves joint outcomes in patients with severe hemophilia A [11],[12],[13],[14], and it is, therefore the standard of care in most developed countries [1],[15]. However, adherence to prophylaxis is poor in some patients [16]. This may be due to the high time burden and inconvenience of a typical prophylaxis regimen, which requires intravenous infusion at least 2 or 3 times per week [17],[18],[19]. Thus, prolonged-half-life FVIII products that allow for less frequent, individualized dosing may increase adherence and ultimately lead to improved clinical outcomes, including prevention of joint disease [20],[21],[22].

In a phase I study of 14 patients, damoctocog alfa pegol had a half-life of ~19 hours versus ~13 hours for sucrose-formulated rFVIII [7]. In the phase II/III PROTECT VIII study [10] safety was comparable to that observed with other FVIII products [23],[24],[25],[26],[27]. Patients and physicians can choose from 3 effective prophylaxis regimens with damoctocog alfa pegol based on individual patient bleeding profile and lifestyle. However, outside of the clinical study, there are currently little real-world safety data on the use of the product.

8. Research questions and objectives

8.1 Primary objective

The primary objective of this study is:

¹ Bayer Data on File

- To assess the long-term safety of prophylaxis with damoctocog alfa pegol in patients with hemophilia A in the real-world setting through the collection and analysis of adverse events (AEs) of special interest including those potentially indicative of PEG accumulation (hypersensitivity reactions, loss of drug effect, renal impairment, neurocognitive disorders, and inhibitor development), AEs, serious adverse events (SAEs), and adverse reactions (ARs).

8.2 Secondary objective(s)

The secondary objective of this study is:

- To monitor the clinical effects of long-term exposure of prophylaxis damoctocog alfa pegol in patients with hemophilia A, including assessments of kidney and liver function parameters, neurological function and patients' PEG plasma levels.

9. Research methods

9.1 Study design

This is a multinational, open-label, prospective, non-interventional, multicenter, cohort study of PTPs with hemophilia A receiving damoctocog alfa pegol as prophylaxis treatment. The study is planned to be conducted in multiple countries in Europe.

At study start, retrospective data will be collected on the patients' baseline characteristics (including genotyping [where available], medical condition and hemophilia treatment history). Also at study start and then at each physician visit during the follow-up phase, data will be recorded on regimens used, AEs of special interest including hypersensitivity reactions, loss of drug effect, renal impairment, neurocognitive disorders, inhibitor development, other AEs, SAEs and drug-related ARs in standard clinical practice. If collected in routine clinical practice at the physician's discretion, parameters relating to kidney and liver function (e.g. creatinine, estimated glomerular filtration rate (eGFR), alanine transaminase (ALT), aspartate aminotransferase (AST), bilirubin), PEG-plasma level and abnormal findings from neurological assessments will be captured in the eCRF/EDC system. Adverse reactions (ARs) relating to the system organ classes of the nervous system and psychiatric disorders will be recorded.

Patients/legal representatives and physicians can choose from different prophylaxis regimens with damoctocog alfa pegol following approved local labels or any other regimen prescribed by the physician as part of normal clinical practice. Patients/legal representatives and physicians can choose to change the dosing regimen based on the patient's response to treatment at any time. A reason for the dose and/or frequency change should be documented.

The planned observation period for each of at least 50 patients will be a minimum of 48 months for the collection of long-term safety data and the prospective monitoring of clinical effects of long-term exposure of prophylaxis with damoctocog alfa pegol in PTPs with hemophilia A.

Due to the observational nature of the study, follow-up visits cannot be scheduled specifically for study purposes and it is unknown when a patient will come for the next visit. Thus, data collection will occur continuously throughout the patient's observational period (i.e., each visit or assessment

as well as AEs reported in the patient diary will be documented in the eCRF/EDC system as they occur). Data collection will continue after 48 months for those patients who are still within the overall study period (i.e. patients initiating follow-up in the first years of the study). Final data collection is planned after 50 patients have been followed-up for a minimum of 4 years. The study will then be terminated for all patients.

Interim reports will be provided annually to the competent authorities as specified in the milestones.

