9.1.1 Primary endpoint

The primary endpoint is:

- Occurrence, duration, treatment, seriousness, and outcome of AEs², SAEs, ARs, and FVIII inhibitor from study start to end of study

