9.2.1.1 Inclusion criteria

- Signed informed consent/assent will be obtained before any study-related activities (i.e. any procedure related to the recording of data according to the protocol)
- PTPs with hemophilia A assigned to Jivi prophylaxis treatment
- Negative FVIII inhibitor test before study entry

² AEs including, but not limited to, hypersensitivity reactions, loss of drug effect, renal impairment, neurocognitive disorders and inhibitor development.

- Decision to initiate treatment with commercially available Jivi has been made by the treating physician before and independently from the decision to include the patient in this study

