10.1 Ethical conduct of the study

This study is a non-interventional study where damoctocog alfa pegol is prescribed in a customary manner in accordance with the terms of the marketing authorization. There is no assignment of a patient to a particular therapeutic strategy. The treatment decision falls within current practice and the prescription of the medicine is clearly separated from the decision to include the patient in the study. No additional diagnostic or monitoring process is required for participation or during the study. Epidemiological methods will be used for the analysis of the collected data.

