10.2 Regulatory authority approvals/authorizations

The study will be carried out within an approved indication in accordance with guidelines and regulations of EMA, FDA, and applicable local law(s) and regulation(s) (e.g., European Union [EU] Regulation No 520/2012 [29]). Recommendations given by other organizations will be followed as well (e.g., European Federation of Pharmaceutical Industries and Associations [EFPIA] [30], European Network of Centers in Pharmacoepidemiology and Pharmacovigilance [ENCePP] [31]).

In addition, the guidelines on Good Pharmacovigilance Practices (GVP module VI [32] and since the study qualifies as a Post-Authorization Safety Study (PASS), GVP module VIII [33],[34]) will be followed.

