11.1 Definitions

An Adverse Event (AE) is any untoward medical occurrence in a patient administered a medicinal product and which does not necessarily have a causal relationship with this treatment. An AE can, therefore, be any unfavorable and unintended sign (e.g., an abnormal laboratory finding), symptom, or disease temporally associated with the use of a medicinal product, whether or not considered related to this medicinal product [35].

The term also covers laboratory findings or results of other diagnostic procedures that are considered to be clinically relevant (e.g., that require unscheduled diagnostic procedures or treatments or result in withdrawal from the study).

- The AE may be:
- A new illness.
- Worsening of a sign or symptom of the condition under treatment or of a concomitant illness.
- An effect of the study treatment.
- An effect of a concomitant medication or treatment.
- Off label use¹¹, occupational exposure, lack of drug effect, medication error, overdose, drug abuse, drug misuse or drug dependency itself, as well as any resulting event.
- An effect related to pre-existing condition improved (unexpected therapeutic benefits are observed).
- Product exposure via mother/father (exposure during conception, pregnancy, childbirth, and breastfeeding).

As mentioned above no causal relationship with a product is implied by the use of the term “adverse event”.

An Adverse Reaction (AR) is defined as a response to a medicinal product which is noxious and unintended. An AR is any AE judged as having a reasonable suspected causal relationship to damoctocog alfa pegol.

Causal relationship: The assessment of the causal relationship between an AE and the administration of treatment is a clinical decision based on all available information at the time of the completion of the eCRF. The assessment is based on the question of whether there was a “reasonable causal relationship” to the study treatment in question. Possible answers are “yes” or “no”.

An assessment of "no" would include:

- The existence of a clear alternative explanation (e.g., mechanical bleeding at the surgical site).

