¹¹ According to GVP Module VI, off label use “relates to situations where the medicinal product is intentionally used for a medical purpose not in accordance with the authorized product information”. Off label use *per se* is an AE, even if no AR is reported, therefore it needs to be ensured that all relevant variables to identify such potential incidents are collected (e.g., indication)

- Non-plausibility (e.g., the patient is struck by an automobile when there is no indication that the product caused disorientation that may have caused the event; cancer developing a few days after the first treatment administration).

An assessment of “yes” indicates that there is a reasonable suspicion that the AE is associated with the use of the study treatment. Factors to be considered in assessing the relationship of the AE to study treatment include:

- The temporal sequence from product administration: The event should occur after the product is given. The length of time from product exposure to the event should be evaluated in the clinical context of the event.
- Recovery on product discontinuation (de-challenge), recurrence on product re-introduction (re-challenge): Patient’s response after de-challenge or patient’s response after re-challenge should be considered in the view of the usual clinical course of the event in question.
- Underlying, concomitant, intercurrent diseases: Each event should be evaluated in the context of the natural history and course of the disease being treated and any other disease the patient may have.
- Concomitant medication or treatment: The other products the patient is taking or the treatment the patient receives should be examined to determine whether any of them may be suspected to cause the event in question.
- The pharmacology and PK of the study treatment: The PK properties (absorption, distribution, metabolism, and excretion) of the study treatment, coupled with the individual patient’s pharmacodynamics should be considered.

An AE or AR is serious (SAE) if it:

- Results in death.
- Is life-threatening.
- Requires in-patient hospitalization or prolongation of existing hospitalization (see exceptions below).
- Results in persistent or significant disability or incapacity.
- Is a congenital anomaly or birth defect.
- Is medically important.

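### The protocol promises use within the authorisation yet admits other regimens and sets no age; because off-label use is itself an AE, the any-AE summary can include patients with no untoward medical event

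*Protocol*

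**What the plan says.** **On authorised use.** Protocol section 10.1 states that "damoctocog alfa pegol is prescribed in a customary manner in accordance with the terms of the marketing authorization". Section 10.2 adds: "The study will be carried out within an approved indication".

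**On who and what is admitted.** Section 9.1 allows regimens "following approved local labels or any other regimen prescribed by the physician as part of normal clinical practice". Section 7.2 gives the approval as age 12 and over. The population criterion in section 9.2.1.1 reads "PTPs with hemophilia A assigned to Jivi prophylaxis treatment", and neither the other inclusion criteria nor the exclusions in 9.2.1.2 mention age or regimen. Section 9.2.1 asks only that local indications be weighed with care, and section 9.2.4 asks for no selection beyond the listed criteria. In Annex 2, checklist item 4.2.2 is ticked as if section 9.1 defined age, but 9.1 states none.

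**On what counts as an AE.** Section 11.1 lists off-label use among the AEs, together with medication error, overdose, misuse and exposure reports. Its footnote says that off-label use per se "is an AE, even if no AR is reported, therefore it needs to be ensured that all relevant variables" to identify it are collected. The same list contains "An effect related to pre-existing condition improved (unexpected therapeutic benefits are observed".

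**On the endpoint.** The primary endpoint in section 9.1.1 begins "Occurrence, duration, treatment, seriousness, and outcome of AEs" and goes on to SAEs, ARs and inhibitors. Section 9.7.3 specifies a patient-level overview of all AEs, then tables by SOC and preferred term (PT).

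**The concern.** There are two linked problems.

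First, a site cannot tell from the text whether a patient on a non-label regimen, or below the label age, belongs in the study. One section says such use does not occur; another admits it.

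Second, the protocol opens the door to such patients and also defines their prescription as an AE. A well patient on a non-label regimen would then enter the any-AE line of the primary analysis because of the prescription alone. Section 11.2 requires seriousness, duration, relationship, action taken and outcome for every AE, and for such a record most of these fields have no clinical meaning. In a cohort of about 60 patients, a handful of these records would move a headline proportion that readers will take as a description of medical events.

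**Working it through.** The claim rests on text, and the plan gives no figure for off-label use. The provisions are compared first; an assumed range then shows the scale.

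**Step 1: do the statements on use conflict?**
- Regimen: section 10.1 says use follows the authorisation. Section 9.1 names label regimens and then, joined by an *or*, any other the physician prescribes. These conflict.
- Age: section 7.2 gives 12 years and over, and sections 9.2.1.1 and 9.2.1.2 give no limit. The advice in 9.2.1 to weigh indications softens the gap but sets no criterion. This conflicts with 10.1 and, as far as age is part of the indication, with 10.2.
- Checklist item 4.2.2 refers to a definition that section 9.1 does not contain.

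**Step 2: does such use become an AE?** Yes. The footnote in 11.1 covers intentional medical use outside the product information, which takes in both regimen and age, and it needs no reaction.

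**Step 3: is it taken out before analysis?** No. Section 11.3 keeps one class out of AE documentation: bleeds not considered causally related, unless they need hospitalisation. Sections 9.1.1 and 9.7.3 make no exception for off-label use or unexpected benefit.

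**Step 4: which outputs are touched?**

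| Output in 9.7.3 | Effect |
|---|---|
| Patient-level any-AE line | Raised |
| SOC total holding the coded term | Raised |
| PT rows for clinical events | Unchanged; off-label use has its own row |
| Special-interest event rates | Unchanged; off-label use is not on the list in 11.3 |
| AR counts | Unchanged; an AR needs a suspected causal link |

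**Step 5: scale, under assumptions.** Inputs: N = 60 (section 9.5); q = share of patients ever off label, assumed 5% to 20%; p = share with a clinical AE, assumed 30% to 70%; p and q taken as independent.
- Patients carrying such an AE: 60q = 60 × 0.05 = 3 to 60 × 0.20 = 12.
- Patients newly entering the any-AE count: 60(1 − p)q.
- Any-AE proportion: p + (1 − p)q.

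| p | q | Any-AE proportion | New patients |
|---|---|---|---|
| 30% | 5% | 33.5% | 2.1 |
| 30% | 20% | 44% | 8.4 |
| 50% | 5% | 52.5% | 1.5 |
| 50% | 20% | 60% | 6.0 |
| 70% | 5% | 71.5% | 0.9 |
| 70% | 20% | 76% | 3.6 |

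Under these assumptions, about 1 to 8 patients are added and the proportion rises by 1.5 to 14 percentage points.

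**The case against.** The best reply is that little of the primary analysis is affected. PT coding isolates off-label use, special-interest events are described separately, and section 11.1 says that the term AE implies no causality. Counting these situations as AEs also serves pharmacovigilance, and section 9.7.1 leaves table layout to the SAP, which is not at hand. All of this stands, and it rules out several stronger readings that a reader might infer:

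- *That the primary endpoint counts prescribing choices as harm.* An AE carries no attribution; the attributed measure is the AR, reported separately.
- *That AE rates move throughout, or that each regimen change adds to the headline.* Only the any-AE line and one SOC total are exposed, and the overview counts patients.
- *That off-label reports would outnumber most clinical PTs.* The 2% in section 9.5 illustrates the chance of seeing at least one event in 50 patients. It is not a typical PT frequency.
- *That the final report could not separate authorised from other use.* Table 2 collects the regimen at every visit and regimen changes continuously, so a split can be derived.
- *That section 10.2 contradicts section 9.1 on regimen.* It speaks of indication. On regimen, only 10.1 conflicts.
- *That the neurological items for children show that patients under 12 are expected.* Ages 12 to 17 are within the stated approval.

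The reply does not remove the conflict between sections 9.1 and 10.1, the missing age criterion, or the AE definition feeding an endpoint without exception. These are protocol text, and a SAP table would not reconcile them.

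**Conclusion.** The point holds in limited form. The protocol contradicts itself on whether use outside the authorisation is part of the study, for regimen and for age, and one checklist reference is wrong. Followed as written, its AE definition and endpoint place patients with no untoward medical event in the any-AE summary and in one SOC total.

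The size cannot be found from the document. The 3 to 12 carriers rest wholly on the assumed 5% to 20%; the number newly counted is smaller because some carriers would have a clinical AE anyway. Nothing suggests that reports of unexpected benefit would be numerous. The study is descriptive, so no test or error rate is at stake. What suffers is the meaning of a headline proportion. The correction is cheap and worth making.

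**What to change.** 1. Reconcile sections 9.1 and 9.2.1 to 9.2.1.2 with section 10.1 (and, for age, 10.2) on which regimens and ages the study covers. This review takes no view on which statement is right.
2. Correct checklist item 4.2.2 so that it points to wherever age is then stated.
3. In 9.1.1 and 9.7.3, state that special situations with no accompanying untoward event (off-label use, medication error, overdose, misuse, exposure reports, unexpected benefit) remain reportable to the MAH but are tabulated separately from clinical AE incidence. Any accompanying medical event is counted under its own term.

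The cost is some wording, one extra table and a slightly lower any-AE count than under full pharmacovigilance counting. Reporting duties and timelines do not change. An on-label/off-label breakdown is optional, needs no new data and can be left to the SAP.
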